5.6.4. Ophthalmological Examination

An ophthalmological examination is performed at Screening (within 28 days prior to TAS-120 administration on Day 1 of Cycle 1) and 4-6 weeks after starting treatment with TAS-120. The ophthalmological examination encompasses external ocular examination, slit lamp biomicroscopy, and dilated ophthalmoscopy. The results of each test, including ad-hoc examinations, will be summarized by scheduled time point. All ophthalmological examination results will be listed in by-patient listings.

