Prior & concomitant medications, AE assessments		→													
Physical examination	X	X				X		X	X		Within 24 hours prior to dosing.				
Vital signs	X	X				X		X	X		Heart rate, blood pressure, body temperature, and respiration rate.				
Height and weight	X	X				X		X	X		Height at screening only.				
ECOG performance status	X	X				X		X	X		Within 24 hours prior to dosing.				
12-Lead electrocardiogram	X	X				X		X	X						
Hematology	X	X	X	X	X	X		X	X		Within 24 hours prior to dosing. More frequent assessments may be performed if clinically indicated				
Coagulation	X	X				X		X	X		Within 24 hours prior to dosing.				
Chemistry (serum or plasma)	X	X	X	X	X	X		X	X		Within 24 hours prior to dosing.				

Evaluation	Screening (Within 28 days of 1 st dose)	Treatment Period (1 cycle =28 days)						Notes	
		Cycle 1			Cycle ≥2				
		D1 (±3 days)	D8 (±3 days)	D15 (±3 days)	D22 (±3 days)	D1 (±3 days)	End of Cycle (±7 days)		
Pregnancy test	X Within 7 days						X		Serum pregnancy test required for WOCBP. Additional testing may be required by local regulations.
Ophthalmological examination	X			See Note					Examination to be performed by an ophthalmologist or qualified delegate at screening, 4-6 weeks after first dose, and as indicated if symptoms or signs of mineral deposits.
PK blood sampling				See Note					Pre-dose (from -30 min to just before dose), 1 h±30 min post-dose, and 3 h±30 min post-dose
ctDNA blood samples	X						X		
Tumor tissue sample	X								Archival or fresh tumor biopsy
Response assessments (CT/MRI)	X						X	X	At baseline and the end of every 2 cycles ±7 days), or as clinically indicated, until radiologic PD or initiation of new anticancer therapy (whichever comes first). For patients who discontinue treatment for reasons other than radiographic disease progression, imaging will be performed at EOT, (if the prior scan was performed ≥9 weeks) and during Survival Follow-up until radiologic disease progression or initiation of new anticancer therapy (whichever occurs first) unless patient withdraws consent.
Survival status								X	For all patients, unless patient withdraws consent or the study is terminated early by the Sponsor.

Table 2: Schedule of Events (Cohort C)

Evaluation	Screening (Within 28 days of 1 st dose)	Treatment Period (1 cycle =28 days)						End of Treatment (+7 days)	Safety Follow-up 30 days after last dose (+7 days)	Survival Follow-up Period (every 12±2 weeks)	Notes				
		Cycle 1				Cycle ≥2									

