		D1 (±3 days)	D8 (±3 days)	D15 (±3 days)	D22 (±3 days)	D1 (±3 days)	End of Cycle (±7 days)		
PET scan	X				See Note				PET scan to be performed at baseline visit, end of Cycle 1 (± 7 days) if baseline is abnormal, and as clinically indicated for response assessment.
Lymph node biopsy	X	See Note							Recommended at baseline visit if lymph node present at baseline and progression
Bone marrow tissue submission	X	See Note							Archival or fresh bone marrow biopsy tissue sample needs to be submitted at baseline visit. In addition, bone marrow biopsy should be performed in case of normalization of peripheral blood count during the futibatinib treatment. In absence of peripheral blood count normalization, biopsy to be performed every 6 months. Additional biopsies to be performed as clinically indicated.
Survival status								X	For all patients, unless patient withdraws consent or the study is terminated early by the Sponsor.

Table 3: Schedule of Events – Study Extension Phase: All Cohorts

	Treatment Period At Least Every 3 Cycles	Safety Follow-up 30 (+7) Days After last Dose	Notes
Physical examination	X	X	Within 24 hours prior to dosing on D1
Vital signs	X	X	Heart rate, blood pressure, body temperature, and respiration rate.
Weight	X	X	
Ophthalmological examination	(X)	X	As needed due to local requirements, physician judgment, and/or symptoms or signs of mineral deposits.
12-Lead electrocardiogram	X	X	
Hematology and coagulation	X	X	Within 24 hours prior to dosing on D1
Chemistry (serum or plasma)	X	X	Within 24 hours prior to dosing on D1
Pregnancy test	X		More frequently if required by local regulations.
Prior & concomitant medications, AE assessments	(X)	X	Collect from the time main informed consent is signed through 30 days after administration of the last dose of study drug or until the start of new anticancer therapy, whichever is earlier.
Response assessments/imaging	(X)		All Cohorts: CT/MRI scans at baseline and the end of every 2 cycles (± 7 days), or as clinically indicated, until radiologic PD or initiation of new anticancer therapy (whichever comes first). Cohort C only: bone marrow, PET, and other response assessments as clinically indicated.

TABLE OF CONTENTS

SUMMARY OF CHANGES.....	2
STUDY SUMMARY	6
Protocol Synopsis	6
Study Schema.....	17
Schedule of Events.....	18
LIST OF ABBREVIATIONS AND DEFINITIONS OF TERMS.....	31
1. INTRODUCTION	35
1.1. Disease Background	35
1.2. Futibatinib (TAS-120)	36
1.2.1. Clinical Overview	36

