Grade 1	
If there is no evidence of ocular toxicity on ophthalmologic examination, continue futibatinib therapy at the same dose level.
 
If diagnosis from ophthalmologic examination is keratitis or retinal abnormality such as central serous retinopathy (CSR)/ retinal pigment epithelial detachments (RPED), withhold futibatinib until signs and symptoms have resolved.
 
If toxicity is reversible (complete resolution or stabilization and asymptomatic) in 4 weeks according to ophthalmologic examination, resume futibatinib therapy at the next lower dose level after consultation with the Sponsor's Medical monitor.
 
Monitor for recurrence every 1 to 2 weeks for a month and as clinically appropriate thereafter. If there is no recurrence then re-escalation can be considered in consultation with the Sponsor's Medical monitor.

Grade 2	
Withhold futibatinib therapy.
 
If there is no evidence of drug-related corneal or retinal pathology on ophthalmologic examination, withhold futibatinib until signs and symptoms have resolved. Resume futibatinib therapy at the next lower dose level.
 
If diagnosis from ophthalmologic examination is keratitis or retinal abnormality, withhold futibatinib until signs and symptoms have resolved or stabilized.
 
If toxicity is Grade 2 and reversible (complete resolution or stabilization and asymptomatic) within 4 weeks according to ophthalmologic examination, resume futibatinib therapy at the next lower dose level after consultation with the Sponsor's Medical monitor.
 
Monitor for recurrence every 1 to 2 weeks for a month and as clinically appropriate thereafter. If there is no recurrence then re-escalation can be considered in consultation with the Sponsor's Medical monitor.

Grade 3	
If the toxicity is Grade 3, report as an SAE and consider permanent discontinuation of futibatinib. If the toxicity is Grade 3 and reversible (complete resolution or stabilization and asymptomatic) within 4 weeks and the patient is receiving clinical benefit, and the Investigator and the Sponsor's Medical monitor agree that re-starting drug is in the best interest of the patient, then futibatinib therapy may be resumed at 2 dose levels lower if appropriate. Monitor for recurrence using appropriate investigations every 1 to 2 weeks for a month and as clinically appropriate thereafter.
 
For cases of recurrence, consider permanent discontinuation.

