6.1. Ophthalmological Examination

The cornea and conjunctiva are readily visible tissues and, therefore, abnormalities of the cornea and conjunctiva can usually be recognized via external ocular examination and routine slit lamp biomicroscopy. The retina is visible through fundoscopy after dilation of the pupil.

Ophthalmologic examination will be performed by an ophthalmologist or qualified delegate at screening and 4-6 weeks after first dose; additional on-study evaluation as needed due to physician judgment and/or symptoms or signs of mineral deposits.

Each evaluation will encompass:

- External ocular examination
- Routine slit lamp biomicroscopy of anterior ocular structures, including the anterior and posterior chambers (Fluorescein or rose Bengal or other dyes used to evaluate the ocular surface can be used according to institutional guidelines and local clinical practice)
- Dilation of the pupil with direct/indirect fundoscopy per institutional guidelines and local clinical practice

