5. STATISTICAL ANALYSIS

5.1. General Methods

Other than exploratory biomarker data, which will be treated differently as explained above, all recorded data will be presented in listings. Data listings will be presented with patient ID and cohort.

Summary tables will be presented for each cohort.

The categorical data will be summarized using frequency counts and percentages of patients, unless otherwise specified.

The continuous data will be summarized using the number of non-missing observation (n), mean, standard deviation, median, minimum value, and maximum value, unless otherwise specified.

Prior anticancer therapy and concomitant medications will be coded with the WHO Drug Dictionary (the most up-to-date version at the time of analysis) and will be summarized by Anatomical Therapeutic Chemical (ATC) Classification level 2 (Therapeutic Main Group) and ATC level 4 (Chemical/Therapeutic Subgroup). Medications and therapies will be sorted in descending order of frequency of ATC level 2 and ATC level 4 within ATC level 2 in the total column. A patient will be counted only once within each level of summarization if the patient has taken a medication more than once. Agents and medications will be reported using the generic name.

For concomitant medications/therapy and adverse events (AEs), the cycle number is determined based on their start/onset dates. For other collected data, the cycle number is determined based on their visit dates. These data include a safety lab test, physical examination, vital signs, weight, ophthalmological exam, Eastern Cooperative Oncology Group (ECOG) performance status (PS), electrocardiogram (ECG), pregnancy test, and scheduled tumor assessment.

If there are multiple laboratory records for a scheduled visit, the one closest to the target date will be used for analysis. If there are two or more records with the same time period to the target date, the record with the latest database entry date will be used for analysis.

CIs for binomial proportions (eg, ORR and DCR) will be derived using the Clopper–Pearson method.

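### SAP 5.6.4 puts ad-hoc eye examinations into the by-time-point table, so the 4-6-week row no longer describes the scheduled examination and may be biased, probably upward

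*SAP*

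**What the plan says.** SAP 5.6.4 names two scheduled eye examinations: one at screening and one "4-6 weeks after starting treatment with TAS-120". It then sets the summary rule, "The results of each test, including ad-hoc examinations, will be summarized by scheduled time point", and adds that every result will be listed by patient.

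The protocol has the same timetable. The Schedule of Events (Tables 1 and 2) calls for examination at screening, "4-6 weeks after first dose, and as indicated if symptoms or signs of mineral deposits". Protocol 6.1 widens the trigger slightly: "additional on-study evaluation as needed due to physician judgment and/or symptoms or signs of mineral deposits". Table 7 in Protocol 5.2.1 adds follow-up after an ocular toxicity: "Monitor for recurrence every 1 to 2 weeks for a month and as clinically appropriate thereafter". For the study extension, the note in Table 3 reads "As needed due to local requirements, physician judgment, and/or symptoms or signs of mineral deposits", although that table also marks an examination at the Safety Follow-up visit.

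Two general rules in SAP 5.1 bear on this. One assigns time: "For other collected data, the cycle number is determined based on their visit dates", and the list of data it covers includes the ophthalmological examination. The other chooses between competing records: "If there are multiple laboratory records for a scheduled visit, the one closest to the target date will be used for analysis". The second is written for laboratory records only. SAP 5.1 also says that categorical data are reported as counts and percentages of patients.

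**The concern.** At the 4-6-week visit every patient still on study is due an examination, whether or not there are complaints. An ad-hoc examination happens because something prompted it. A percentage that combines the two describes neither group: it is not the finding rate at the scheduled visit, and it is not the rate among patients sent for an extra examination.

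This matters because ocular toxicity leads to dose holds, reductions and discontinuation under Table 7, and a reader of the study report will look to the eye-examination table for what routine examination found. If later time points appear in the table, they will consist mainly of patients chosen for examination. A higher percentage there could then be read as toxicity building up over time when it only reflects who was examined.

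**Working it through.** The plan states no ocular finding rate, no expected number of ad-hoc examinations and no precision target for this table, so there is no figure to reproduce. The check is first on the wording, then on a labelled illustration.

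**1. Where can an ad-hoc result go?** There are two readings.
- *Only the scheduled time points named in SAP 5.6.4.* These are screening and 4-6 weeks. A post-baseline ad-hoc result then enters the 4-6-week row or has no row at all.
- *Cycle by visit date, as in SAP 5.1.* Four weeks after the first dose is Day 4×7+1 = 29, and six weeks is Day 6×7+1 = 43. With 28-day cycles, Cycle 2 runs from Day 29 to Day 56. The scheduled examination falls in Cycle 2, and any ad-hoc examination on Days 29-56 shares its row. Rows for later cycles contain mainly patients selected for examination.

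Neither reading gives a row made up of the scheduled examination alone.

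**2. Is there a rule for which record counts?** The closest-to-target rule covers laboratory records only. SAP 5.6.4 gives no window for mapping an ad-hoc examination to a time point, and does not say which result stands when a patient has two.

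**3. How are other safety data handled?** SAP 5.6.3 describes laboratory values at scheduled visits and lets unscheduled results feed the worst post-baseline grade. SAP 5.6.6 gives ECG a by-time summary plus a shift to the worst post-baseline interpretation. SAP 5.6.4 puts ad-hoc results into the by-time table and plans no worst post-baseline summary.

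**4. What could it do to the percentage?** SAP 5.1 counts patients, so the illustration does too. All three inputs are assumptions:
- *p*: finding rate at the scheduled examination
- *a*: share of those patients who also have one ad-hoc examination mapped to the same row
- *q*: finding rate at the ad-hoc examination

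If a patient counts as positive on any finding, and the two results are independent, the reported rate is p + (1 − p)·a·q. For p = 10%, a = 10% and q = 50% this is 0.10 + 0.90×0.10×0.50 = 14.5%. Results for p = 10%:

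| a | q = 0 | q = 50% | q = 80% |
|---|---|---|---|
| 5% | 10.0% | 12.3% | 13.6% |
| 10% | 10.0% | 14.5% | 17.2% |
| 20% | 10.0% | 19.0% | 24.4% |

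Over the same a = 5-20% and q = 50-80%, p = 5% gives 7.4-20.2% and p = 20% gives 22.0-32.8%.

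Independence is generous to the concern. If every lesion seen ad hoc is also seen at the scheduled examination, nothing is added and the reported rate stays at p. For p = 10% the illustration therefore runs from 10.0% to 24.4%, and the documents do not say where in that range the trial would fall.

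**The case against.** A reader might infer that the 4-6-week rate *is* inflated, and by a calculable amount. For example, take 9 findings in 90 scheduled examinations (10.0%) and add 10 ad-hoc examinations with half abnormal: (9+5)/(90+10) = 14.0%. Adding 20 with 60% abnormal gives (9+12)/(90+20) = 19.1%. The documents do not support that inference, for four reasons.

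- The arithmetic counts examinations, whereas SAP 5.1 calls for percentages of patients. An ad-hoc examination in someone already among the 90 leaves the denominator at 90.
- Every input is assumed.
- The direction is not certain. Some ad-hoc examinations are recurrence checks under Table 7 and may be normal. Counted per examination, 10 normal checks added to 10 findings in 100 examinations would lower the rate to 10/110 = 9.1%. Counted per patient on any finding, they would leave it at 10.0%.
- If the visit-date rule governs, examinations outside Cycle 2 do not touch the row. A closest-to-target choice, if extended to eye data, would limit the effect further.

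Nor is the scheduled examination a pure measure of asymptomatic findings. It includes patients with symptoms and misses those who left earlier, and no study objective asks for that estimate. Dose decisions follow each patient's own toxicity, not this table. Ocular adverse events are also covered by the adverse-event tables in SAP 5.6.2, and the listings keep every examination.

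These points stand, and they limit the claim to possible bias in one table. They do not repair the rule: on either reading of the SAP, results from selected examinations sit beside those from the scheduled one.

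**Conclusion.** The point holds in a limited form. By its own wording, SAP 5.6.4 mixes selected and systematic examinations, and no other provision separates them. The 4-6-week row therefore does not estimate the finding rate at the only fixed on-treatment examination in the main study. It may be biased, probably upward, on the assumption that examinations prompted by symptoms or signs show findings more often than routine ones. Any later rows would describe mainly patients selected for examination and should not be read as a time trend.

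The size cannot be derived from the documents, and the percentages above are illustrations only. The consequence is confined to a descriptive safety table. This is a cheap improvement to the SAP.

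**What to change.** In SAP 5.6.4, replace the summary sentence with a rule to this effect:

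- Summarize only the scheduled examinations (screening and 4-6 weeks after the first dose) by time point, with the patients examined at that visit as denominator.
- Do not assign ad-hoc examinations to a scheduled time point.
- Include ad-hoc examinations, together with the scheduled post-baseline one, in a per-patient summary of the worst post-baseline finding, with the All Treated Population as denominator.
- Keep all examinations in the by-patient listings, as already planned.

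This follows the approach that SAP 5.6.3 already takes for laboratory data. The cost is one SAP sentence and one extra table. No new data are needed, and no examination schedule or dose rule changes.

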5.6.5. Vital Signs and Weight

Vital sign measurements include systolic blood pressure, diastolic blood pressure, pulse rate, respiration rate, and body temperature. Each vital sign parameter will be summarized with descriptive statistics by scheduled time point. Change from baseline will be summarized in a similar manner.

Weight at each scheduled time point and change from baseline will be summarized with descriptive statistics by scheduled time point. Weight will be displayed in kilograms. Height, collected only at baseline, will be displayed in centimeters. Body temperature will be displayed in Celsius.

All vital sign data will be presented in by-patient listings.

5.6.6. Electrocardiograms

ECG measurements include HR, RR interval, QT interval and its Fridericia's correction and Bazett's correction, and clinically abnormal findings. QTcF (Fridericia's correction) is calculated as $QT/RR^{0.33}$. QTcB (Bazett's correction) is calculated as $QT/RR^{0.5}$. Each ECG parameter will be summarized with descriptive statistics by scheduled time point. Changes from baseline will be summarized in a similar manner.

Shift tables will present changes from baseline in ECG interpretation (categorized as normal, abnormal not clinically significant, abnormal clinically significant) to the worst post-baseline result.

In addition, the number and percentage of patients with at least one post-baseline abnormal ECG result in QTcF during on-treatment period will be summarized. Clinically abnormal ECG results in QTcF will be categorized as follows:

Absolute QTcF interval prolongation:

- QTc interval \leq 470 ms
- QTc interval >470 - 480 ms (with baseline QTc interval \leq 470)
- QTc interval > 480 - 500 ms (with baseline QTc interval \leq 480)
- QTc interval > 500 ms (with baseline QTc interval \leq 500)

Change from baseline in QTcF interval:

- QTC interval increases from baseline \leq 30 ms
- QTC interval increases from baseline 30 - 60 ms
- QTC interval increases from baseline > 60 ms

All ECG data will be presented in by-patient listings.

5.6.7. Physical Examination

The physical examination will be performed during the Screening period, on Day 1 of each cycle of the Treatment Period, at the End of Treatment, and at 30-day Safety Follow-up.

The physical examination data will be presented in by-patient listings.

5.6.8. ECOG Performance Status

The ECOG PS score will be obtained during the Screening period, on Day 1 of each cycle of Treatment Period, at the End of Treatment, and at 30-day Safety Follow-up. The ECOG PS scores and the grades from 0 to 5 are described in [Table 19](#) :

Table 19: Grade Categories of Eastern Cooperative Oncology Group Score

GRADE	ECOG
0	Fully active, able to carry on all pre-disease performance without restriction.
1	Restricted in physically strenuous activity but ambulatory and able to carry out work of a light or sedentary nature; eg, light house work, office work.
2	Ambulatory and capable of all self-care but unable to carry out any work activities. Up and about more than 50% of waking hours.
3	Capable of only limited self-care, confined to bed or chair more than 50% of waking hours.
4	Completely disabled. Cannot carry on any self-care. Totally confined to bed or chair.
5	Dead.

The ECOG performance status score will be summarized with descriptive statistics by scheduled time point. A shift table will be presented to display the shift from baseline grade to the worst post-baseline grade.

5.6.9. Pregnancy Test

If the patient is female and of childbearing potential, a serum or urine β -HCG pregnancy test will be performed during Screening Period and at the End of Treatment. Pregnancy test result will be presented in by-patient listing.

5.7. Pharmacokinetic Analyses

Blood samples will be collected for PopPK analysis, including estimation of steady-state exposure such as area under the curve. The samples will be used to determine concentrations of futibatinib in plasma. Detailed analytical procedures will be described in the independent SAP for PopPK.

The listing of futibatinib plasma concentration will be provided.

5.8. Pharmacodynamic/Biomarker Analyses

Biomarkers, including *FGFR* and, possibly, other genetic variants other than those which were listed above as criteria for eligibility, will be investigated on exploratory basis and will not be listed in this formal SAP.

5.9. Interim Analyses

The interim analysis will be performed in Cohort A at the time when there are 35 response evaluable patients in the cohort in order to determine if the cohort should continue. During interim analysis, the Sponsor will review the data and perform statistical analyses on the primary efficacy endpoint.

Because Cohort A is based on a 2-stage Simon design, the overall type I error is controlled for the interim analysis. There is no need for type I error adjustment or sample size adjustment. Because this is open label study, there is no blinding/unblinding. Therefore there is no need for maintaining blinding during the interim analysis.

